### **2.2 Study Objectives**

The objective of the study is to evaluate the usability of the Rapid SARS-CoV-2 Antigen Test in a home setting. The main focus will be to assess the clarity and robustness of the instructions for use.

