## 4.0 Study Design

This is a clinical study to evaluate the feasibility of using anterior nasal (AN) swabs on Rapid SARS-CoV-2 Antigen Test kits for OTC use in symptomatic and asymptomatic individuals following recommendations from the FDA's July 29, 2020 Template for Manufacturers of Molecular and Antigen Diagnostic COVID-19 Tests for Non-Laboratory Use, Section J 7. EDP Biotech Corp. will recruit subjects for an at home human usability study through the internet as well as by referral throughout the United States. Rapid SARS-CoV-2 Antigen Test specimen collection and testing will be done under the supervision of EDP Biotech Corp. either in person or via video conference. Testing will be observed by EDP Biotech Corp. medical professionals or designees either in person or via video conference. The study subjects shall perform the entire workflow including sample collection, testing, and results interpretation. Following results interpretation, subjects will complete a usability and ease of use questionnaires. The data collected in study may be submitted as a regulatory filing to the US FDA or other agencies. All specimens will be collected from participating consenting subjects. Additional testing of the specimens for research purposes may be performed. The study acceptance criteria is a 95% success rate for subjects producing the control line on the Rapid SARS-CoV-2 Antigen Test and a SUS average score of 68 or greater.

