### 4.3 Specimen Collection

Each potential subject will be asked to complete a form describing any symptoms of respiratory illness being experienced, education level, and basic demographics (Appendices 2 and 3). Subjects will be observed by EDP Biotech Corp. personnel or

designees during sample collection, testing, and shipment preparation either in person or via video conference.

Each study volunteer who agrees to participate in the study will be asked to complete an Informed Consent Form (Appendix 6). A parent or guardian will need to consent for subjects under 18 years old. Study subjects between the ages of 7 and 17 years old will be asked to complete an Assent form (Appendix 7). Specimens will be collected and tested only after the Informed Consent form is completed. Each study volunteer will be assigned a unique specimen identification number (SID). The Clinical Investigators or designees will observe AN swab collection and testing. Subjects will collect AN swab samples and perform the Rapid SARS-CoV-2 Antigen Test using only the IFU for instruction or video linked from the IFU. The collection devices and storage tubes will be appropriately labeled with the SIDs and not the names of the participants to maintain confidentiality.

Rapid SARS-CoV-2 Antigen Test AN swab specimens will be collected and tested per the product directions that accompany the device (Appendix 1). Following Rapid SARS-CoV-2 Antigen Test, subjects will complete a System Usability Scale questionnaire (Appendix 4) and an Ease of Use assessment including interpretation of mock test cassettes (Appendix 5).

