#### **4.4 Sample Types and Numbers**

Subjects will be enrolled in an “all comers” style, including both symptomatic and asymptomatic patients. The study population will include subjects from 2 years old to greater than 65 years old. Minors must be consented by their parent or legal guardian. The parent or legal guardian should collect the samples and perform testing if the child is between 2 and 13 years old. Older children ages 14-17 should collect their samples and perform their tests without their parent or legal guardian intervening. The study will include two sections, 50 subjects testing themselves and 50 subjects testing another person such as children between the ages of 2 and 13 years old. Enrollment efforts in various zip codes will be pursued in order to represent different socioeconomic and educational backgrounds and this information will be captured in the tester questionnaire (Appendix 2) and subject questionnaire (Appendix 3). A portion of the study population should include Spanish speaking users. High risk individuals will not be excluded. Participants who regularly use home diagnostic tests, such as glucose meters, will be excluded. Study testing will continue until the full range of 2-65+ ages are tested including at least 50 self-tests and 50 tests performed by subjects on other participants.

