### 6.2.1 Acceptability of Data for Analysis

Valid individual specimen results generated in invalid runs are not acceptable for inclusion in final data analysis. Samples tested in invalid runs must be re-tested if the remaining specimen volume is available. Only valid results from specimens in valid runs will be included in the final data analysis.

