### 6.2.2 Exclusion of Data from Analysis

Data from invalid runs results will be excluded. All excluded results will be documented with rationale for exclusion and a summary of these cases will be provided.

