## 9.0 Risk Analysis

This is a non-significant risk device study. The study presents no potential for serious risk to the health, safety, or welfare of any human subject as it uses only commonly employed techniques for the AN swab specimens. There will be subject recruitment at the EDP Biotech Corp. investigative site using public posting, e-mail correspondence, and referrals. Study results will be used to demonstrate that the Rapid SARS-CoV-2 Antigen Test technique is suitable for home use without a prescription.

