## 10.0 Study Master File (SMF)

The Clinical Investigator (CI) or Designee(s) will collect and review copies of the required essential documents (ED) listed below in the form of a Study Master File (SMF). EDP Biotech Corp. is the sponsor of the study and will maintain the SMF and copies of the required EDs; the Investigator Site File (ISF) will contain original documents.

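### Section 4.4 leaves sponsor and kit-maker staff, and medically or laboratory-trained people, eligible as testers, so the mean SUS may overstate how clear the IFU is to lay users

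*Protocol*

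**What the plan says.** Section 2.2 of the protocol sets the target: "The main focus will be to assess the clarity and robustness of the instructions for use". Section 4.3 has testers collect the swab and run the test "using only the IFU for instruction or video linked from the IFU", then complete the SUS questionnaire. Section 4.0 makes the result a pass rule: a control-line success rate of 95% "and a SUS average score of 68 or greater".

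On who may take part, section 4.4 describes all-comers enrolment and a minimum of 50 self-tests and 50 tests on another person. It seeks a spread of zip codes, education and socioeconomic background, with some Spanish speakers. It names one exclusion: "Participants who regularly use home diagnostic tests, such as glucose meters, will be excluded".

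On recruitment, section 4.0 uses the internet and referral across the United States. Section 9.0 adds: "There will be subject recruitment at the EDP Biotech Corp. investigative site using public posting, e-mail correspondence, and referrals". Section 10.0 states that "EDP Biotech Corp. is the sponsor of the study", so the recruiting organisation is also the sponsor.

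Sections 4.3 and 7.2 list education, race and ethnicity, zip code and language among the data collected. Occupation, training and affiliation are not listed. The tester form itself (Appendix 2) is not shown.

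**The concern.** The exclusion in 4.4 only makes sense if prior familiarity with home testing weakens the evidence that the IFU alone is enough. That reasoning is applied to one group. A glucose-meter user is kept out. A laboratory worker who handles similar tests, or an employee who already knows this kit, may take part as a tester and contribute a SUS score to the mean.

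Such a tester may rate the kit as easy because of what he or she already knows, so the rating says little about whether the IFU is clear. The provisions on zip code, education and language widen the pool but keep neither group out. At stake is whether a mean SUS of 68 or more can be read as evidence about lay users. Section 9.0 needs that reading, because the results are to support home use without a prescription. Eligibility is fixed in the protocol. If affiliation and training are never recorded, no later analysis can separate these testers.

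**Working it through.** The protocol gives no SUS standard deviation, no expected mean, no share of trained or affiliated testers and no derivation of the sample size. There is therefore no figure of its own to reproduce, and what follows is a sensitivity range.

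**Inputs from the protocol.** SUS threshold 68 (section 4.0). Minimum number of tests 50 + 50 = 100 (section 4.4), taken as 100 SUS scores, one per test.

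**Assumed inputs.** Share *f* of trained or affiliated testers: 5%, 10%, 20%. Amount *d* by which their SUS exceeds that of lay testers: 5 to 15 points. SD of SUS: 15 or 20. Lay true mean *m*: 64, 66 or 70.

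**Shift in the mean.** Overall mean = (1 − *f*)·*m* + *f*·(*m* + *d*) = *m* + *f*·*d*. The shift is *f*·*d*, and the lay mean that still gives an overall mean of 68 is 68 − *f*·*d*.

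| Share *f* | Shift, *d* = 5 | Shift, *d* = 10 | Shift, *d* = 15 | Lay mean that still gives 68 |
|---|---|---|---|---|
| 5% | 0.25 | 0.50 | 0.75 | 67.25 to 67.75 |
| 10% | 0.50 | 1.00 | 1.50 | 66.5 to 67.5 |
| 20% | 1.00 | 2.00 | 3.00 | 65 to 67 |

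**Chance of passing.** With a normal approximation, P(mean SUS ≥ 68) = 1 − Φ[(68 − *m* − *f*·*d*) / (SD/√100)]. With *d* = 10:

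| Lay mean, SD | *f* = 0 | *f* = 5% | *f* = 10% | *f* = 20% |
|---|---|---|---|---|
| 66, SD 15 | 0.091 | 0.159 | 0.252 | 0.500 |
| 66, SD 20 | 0.159 | 0.227 | 0.309 | 0.500 |

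For example, at *m* = 66, SD 15 and *f* = 5%: (68 − 66 − 0.5)/1.5 = 1.0, and 1 − Φ(1.0) = 0.159. Adding the extra variance from mixing two groups, *f*(1 − *f*)*d*², changes these values by at most about 0.005.

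**Away from the threshold** (SD 15, *d* = 10):

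| Lay mean | *f* = 0 | *f* = 5% | *f* = 10% |
|---|---|---|---|
| 64 | 0.4% | 1.0% | 2.3% |
| 70 | 91% | 95% | 98% |

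At modest shares, the pass or fail result rarely changes unless the lay mean is close to 68.

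**The case against.** The strongest reply is that this is a choice of population. The product is for over-the-counter sale, the intended use in section 1.2 sets no limit on the user's training, and nurses and laboratory workers buy such tests too. An all-comers sample may properly include them. This has force for trained testers and is a real cost of excluding them. It has less force for employees of the sponsor or kit maker, who may know this particular kit.

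Second, recruitment is broad: internet, public posting, e-mail and referral, across the country. Where the protocol gives sponsor personnel a role in testing, they are observers. A reader might infer from recruitment at the sponsor's own site that staff are meant to be enrolled. The documents do not support that. They leave staff enrolment possible and do not show that it is planned or likely.

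Third, the size and even the upward direction are assumed. That is correct, and it limits the weight of the point.

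Fourth, Appendix 2 is not shown, and section 7.2 does not present its list of items as complete, so the form may already ask about training. Asking would help to identify these testers but would not exclude them.

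A reader might also infer that the 95% control-line criterion is inflated in the same way. The documents do not establish this. Section 6.2.1 states "Only valid results from specimens in valid runs will be included in the final data analysis", section 6.2.2 states "Data from invalid runs results will be excluded", and section 6.2.5 has invalid results repeated. If a missing control line is handled as an invalid result under these rules, the tester's training adds little or nothing to that rate. The point is therefore confined to the SUS.

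**Conclusion.** The gap is in the text: one experienced group is excluded, while people with medical or laboratory training and staff of the sponsor or kit maker may act as testers. Because the study judges an IFU used as the only instruction, the mean SUS may overstate the clarity of the IFU for lay users.

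How much is unknown. Under the assumed differences of 5 to 15 points the shift is 0.25 to 0.75 points at a 5% share and 1 to 3 points at 20%. This rests on assumed shares and differences, and on the untested premise that such testers score higher. It could change the conclusion mainly if the lay mean is close to 68. The point does not show that the SUS criterion would be passed wrongly. It is an inexpensive improvement for the sponsor to consider.

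**What to change.** Extend the exclusion sentence in section 4.4 so that employees of the sponsor or kit manufacturer, and people with medical or laboratory training, may not act as testers. Screen for this at enrolment, for example with a question on the tester form (Appendix 2) if it does not already ask. The bar applies to testers only: where one person tests another, the person being swabbed need not be excluded.

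The cost is one sentence and a screening question or two, slightly slower recruitment, and a sample that omits some trained over-the-counter buyers whom section 1.2 does not rule out.

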#### **6.2.5 Invalid Results**

Invalid results will be repeated either by the same subject or a different subject until the criteria found in section 4.4 is met.

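### Do one pooled 95% control-line rate and one SUS average, with open-ended section sizes, let the recruited mix decide the result?

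*Protocol*

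**What the plan says.** Section 4.0 states the acceptance criteria once, for the whole study: "The study acceptance criteria is a 95% success rate for subjects producing the control line on the Rapid SARS-CoV-2 Antigen Test", together with "a SUS average score of 68 or greater". It does not mention the two sections.

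Section 4.4 gives the plan: "The study will include two sections, 50 subjects testing themselves and 50 subjects testing another person". The same paragraph ends by making both counts minimums, since testing goes on "until the full range of 2-65+ ages are tested including at least 50 self-tests and 50 tests performed by subjects on other participants". It sets no upper limit, no ratio and no quota per age band.

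Age and section are partly tied. Children aged 2 to 13 should be tested by a parent or guardian, and for adolescents 4.4 says: "Older children ages 14-17 should collect their samples and perform their tests without their parent or legal guardian intervening". Section 6.2.5 adds: "Invalid results will be repeated either by the same subject or a different subject until the criteria found in section 4.4 is met".

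No part of sections 4 or 6 says whether the criteria apply to all testers together, to each section, or to a weighted combination. Section 6.3.1, despite its heading, deals only with transcription.

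**The concern.** The pass rule is fixed, but the composition of the sample it applies to is not. A pooled rate or mean is a weighted average with weights equal to the section sizes. If testing oneself and testing another person succeed at different rates, enlarging the better section lifts the pooled figure and enlarging the worse one lowers it.

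Enrolment continues until the age range is covered, and minors belong to one section by age, so filling a gap among minors would add to one section only. Section 9.0 says the results are to show suitability for home use without a prescription. A weak result in people testing others, half the planned design, could thus be diluted by surplus self-testers.

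**Working it through.** **Inputs.** Thresholds of 95% and 68 come from Protocol 4.0, and minimum sizes of 50 and 50 from 4.4. The protocol gives no derivation of the sizes, no error rate and no section-specific rates or means, so there is no stated figure to reproduce. All section rates and means below are assumptions. Sizes are written self + other. Each tester is counted once; how repeats under 6.2.5 are counted is a separate question.

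**1. Pooled rate for fixed section results.** Pooled = (n1·p1 + n2·p2)/(n1 + n2). With 98% and 90%:
- 50+50: (49 + 45)/100 = 94.0%
- 60+50: (58.8 + 45)/110 = 94.4%
- 100+50: (98 + 45)/150 = 95.3%
- 150+50: (147 + 45)/200 = 96.0%
- 50+100: (49 + 90)/150 = 92.7%

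The switch needs 0.98n + 45 ≥ 0.95(n + 50), so n ≥ 2.5/0.03 = 83.3: at least 84 self-testers, 34 above plan.

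**2. Pass probability under pooling.** This is P(X1 + X2 ≥ ceil(0.95N)) with independent binomials. The required totals are 95 (50+50), 105 (60+50 and 50+60), 119 (75+50), 143 (100+50 and 50+100) and 190 (150+50).

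| Assumed true rates, self/other | 50+50 | 60+50 | 75+50 | 100+50 | 150+50 | 50+60 | 50+100 |
|---|---|---|---|---|---|---|---|
| 98/88% | 0.286 | 0.261 | 0.367 | 0.446 | 0.712 | 0.158 | 0.045 |
| 99/90% | 0.525 | 0.507 | 0.648 | 0.750 | 0.941 | 0.358 | 0.165 |
| 97/92% | 0.526 | 0.474 | 0.565 | 0.599 | 0.768 | 0.392 | 0.259 |
| 98/96% | 0.92 | 0.90 | 0.94 | 0.95 | 0.99 | 0.87 | 0.87 |
| 97/97% | 0.919 | 0.886 | 0.917 | 0.917 | 0.960 | 0.886 | 0.917 |

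The bottom row has no mix effect at all; it moves only through sample size and rounding. The dip at 110 testers arises because 0.95 × 110 = 104.5 rounds up to 105, so five failures are allowed, as at 100 testers.

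**3. Comparison with equal weighting.** The alternative rule is (x1/n1 + x2/n2)/2 ≥ 0.95. At 50+50 it is identical to pooling. At 60+50 it gives 0.261, 0.507 and 0.474 for the first three rows, the same as pooling. At 50+60 it gives 0.213, 0.461 and 0.424, so there pooling is the stricter rule. The equal-weight rates in those rows are 93%, 94.5% and 94.5%, all below 95%, so the extra strictness does not let a weak result through. At 150+50 with 98/88% equal weighting gives 0.226 against 0.712; the difference is large only at such sizes.

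**4. Lowest passing count in a smaller section of 50.** This is ceil(0.95N) − n1: 45 at 50+50, 105 − 60 = 45 at 60+50, 119 − 75 = 44, 143 − 100 = 43, and 190 − 150 = 40 at 150+50. Each applies only if the larger section has no failures. At a true 98%, 150 out of 150 has probability 0.98^150 = 0.048.

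**5. SUS.** With assumed section means of 72 and 62, the pooled mean is 67.0 at 50+50, (4320 + 3100)/110 = 67.5 at 60+50, 68.0 at 75+50, 68.7 at 100+50 and 65.3 at 50+100. The switch needs 72n + 3100 ≥ 68(n + 50), so n ≥ 300/4 = 75 self-testers.

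**6. How far could the sizes drift?** Section 4.4 sets no age quotas, so a gap may need only a few people. It offers young children only as an example of the other person, so adults up to 65+ can be tested in either section. The tie between age and section therefore follows from the text only for minors. Those aged 2 to 13 would be expected to enter while the 50 tests on others are being filled. Section 6.2.5 treats the 4.4 counts as the target to be reached.

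**The case for a change.** The strongest case for a change is that this is more than an analysis detail left to another document. The protocol itself fixes the pass rule and itself leaves the composition open, and the two interact. The pass probabilities are correct, the drift runs in both directions, and a sentence in 4.0 would cost no subjects.

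The textual premises stand: one criterion each, no combination rule, sizes as minimums. The arithmetic stands too, given its assumptions. Two things weaken it. First, the effect needs two conditions together, neither supported by the protocol: sections on opposite sides of the threshold, and one section far above plan. Section 1.4 describes the control line as a check on specimen volume and wicking, and the protocol gives no reason for a ten-point gap according to whose nose was swabbed.

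Second, the obvious remedy is not clearly better. Equal weighting leaves the sizes in 4.4 open and does not remove the drift: at 98/88% it ranges from 0.18 (50+100) to 0.29 (50+50). It also costs a good device something at 150+50: 0.928 against 0.960 at a true 97%. A 90% floor per section would add nothing to it, because an equal-weight average of at least 95% with neither rate above 100% already forces both to at least 90%. Requiring 95% in each section is a different, stricter design: at 50+50 and a true 97% it cuts the pass probability from 0.92 to 0.66.

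**Conclusion.** No change follows. Read plainly, 4.0 asks for one rate and one mean over all testers, and 4.4 plans equal sections. Followed as written, the plan gives the decision that equal weighting would give. It gives practically the same decision with ten extra self-testers, and a somewhat stricter one with ten extra tests on others.

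Pooling could mislead in the device's favour only with roughly 75 or more self-testers against 50 and section performance straddling the threshold. The size of that effect (for example 0.286 rising to 0.712) rests wholly on assumed rates.

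The choice among pooled, equal-weight and per-section criteria is a fair matter of judgement, and stating the combination rule is commonly left to a statistical analysis plan, which is not at hand here. Reporting each section's control-line rate with its exact interval, and its SUS mean, would expose any dilution; the report foreseen in section 6.2 leaves room for it. The conclusion would need another look only if the sections closed very unequal.

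### The rules for invalid results (6.2.1, 6.2.2, 6.2.5) can remove the very failures that the 95% control-line criterion in 4.0 is meant to count; 4.4 also does not say that each tester counts once.

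*Protocol*

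**What the plan says.** Section 4.0 sets two acceptance criteria. The one at issue is a "95% success rate for subjects producing the control line"; the other is a mean SUS score. The unit of the first is the subject.

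Three later rules decide which results reach the analysis:

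- 6.2.1: "Only valid results from specimens in valid runs will be included in the final data analysis".
- 6.2.2: "Data from invalid runs results will be excluded". Exclusions must be documented with a reason and summarised.
- 6.2.5: "Invalid results will be repeated either by the same subject or a different subject until the criteria found in section 4.4 is met". No limit on repeats is given.

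Section 4.4, to which 6.2.5 points, gives the size twice. It plans in people: "The study will include two sections, 50 subjects testing themselves and 50 subjects testing another person". It then continues testing until the age range is covered, "including at least 50 self-tests and 50 tests performed by subjects on other participants". It also says: "The parent or legal guardian should collect the samples and perform testing if the child is between 2 and 13 years old".

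Section 1.4 describes the control line as the procedural control, showing that enough specimen was added and that the membrane is wicking. Section 2.2 makes the clarity and robustness of the instructions for use the main focus.

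**The concern.** In a usability study, a tester who follows the instructions and gets no control line is the failure of interest. For most lateral-flow tests, and on the natural reading of 1.4, that is also an invalid result. If so, one event is a failure under 4.0 and a reason for exclusion and repetition under 6.2. The protocol does not say which rule prevails for the 95% rate.

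If the 6.2 rules prevail, the criterion cannot tell clear instructions from poor ones, because the results that would make it fail have been taken out. A repeat by the same tester is moreover a use after practice. It says less about whether the instructions alone are enough. Section 9.0 intends the results to show suitability for home use without a prescription, and 4.0 foresees a regulatory submission, so the rate should mean first-use success.

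The wording of 4.4 raises a smaller question about the same rate. If tests rather than testers are counted, one adult can supply more than one of the 50 in the section testing others.

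**Working it through.** **No sample-size calculation to reproduce.** The protocol gives no assumed success rate, power or precision target behind 50 + 50. The check is therefore a reading of the rules, followed by binomial probabilities on assumed rates.

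**Inputs.** From the protocol: 50 + 50 = 100 testers if each does one test (4.4), and a criterion of 95% (4.0), read here as at least 95 of 100. Assumed: the true first-attempt success rate *p*, shown over a range.

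**Step 1: the 6.2 rules applied as written, with a missing line taken as invalid.**

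- A first attempt without a control line is invalid and is excluded (6.2.1, 6.2.2).
- It is repeated by the same or another subject (6.2.5). A failed repeat is invalid too, so it is also excluded and repeated.
- Repetition ends when 4.4 is satisfied.

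Every retained result then has a control line: retained rate = 100/100 = 100% for any *p*. Only the number of attempts changes. The expected number is 100/*p*: about 109 at *p* = 0.92, 111 at 0.90 and 125 at 0.80.

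For example, 92 successes in 100 first attempts miss the criterion (92 < 95). Once the 8 failures have been replaced by valid repeats, the retained set reads 100/100.

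**Step 2: first attempts scored, failures kept.** P(pass) = P(X ≥ 95), with X ~ Binomial(100, *p*):

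| Assumed *p* | P(pass), first attempts | Retained rate under step 1 |
|---|---|---|
| 0.80 | < 0.0001 | 100% |
| 0.85 | 0.002 | 100% |
| 0.90 | 0.058 | 100% |
| 0.92 | 0.180 | 100% |
| 0.97 | 0.919 | 100% |

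The two ways of scoring differ most where the instructions fall short of 95%.

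**Step 3: tests against testers in 4.4.** As an extreme case, 25 parents with two children each supply 25 × 2 = 50 tests, of which 25 are second uses. The figures below apply only if failures are kept in the rate; if they are dropped, practice cannot move a rate already at 100%. With *n*₁ first uses at *p* and *n*₂ second uses at *p*₂, the pass probability comes from the sum of two binomials:

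- *p* = 0.97, *p*₂ = 0.99: 0.92 with no second uses, 0.94 with 10, 0.96 with 25.
- *p* = 0.92, *p*₂ = 0.94 to 0.99: 0.18 with no second uses, 0.20 to 0.25 with 10, 0.23 to 0.40 with 25.

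The protocol gives no information on the size of a practice effect.

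**Step 4: does anything else settle the count?** Section 4.3 says: "Each study volunteer will be assigned a unique specimen identification number (SID)". Two children tested by one parent are two volunteers with two numbers, so this does not limit the tester to one. The tester form in 7.2 identifies testers and would allow them to be counted, but it sets no counting rule.

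**The case against.** **The rules in 6.2 may not reach a missing control line.** Sections 6.2.1 and 6.2.2 speak of invalid runs and of retesting if specimen volume remains, which is laboratory language. An invalid result is not defined, and Appendix 1, which may define it, is not shown. Section 6.2.5 could be meant only to top up numbers, with a missing line still scored as a failure; otherwise the 95% criterion could hardly fail, which the sponsor cannot have intended. This stands as a limit on the claim. A reader might infer that the plan is bound to report 100%. The documents do not support that, because it needs an inference about what counts as invalid. They equally contain no sentence that keeps such failures in the rate, and the rules as written point the other way.

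**The exclusions are visible.** Section 6.2.2 requires them to be documented and summarised, so the first-attempt rate could probably be recovered. True, but nothing makes that recovered rate the one judged against 95%.

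**Section 4.4 does not contradict itself.** With one test per tester, both of its sentences hold, and the criterion and the tester form are both per person. A reader might infer that the change from subjects to tests by itself undermines the result. It does not. The section testing others is not confined to parents, the case of 25 parents with two children each is extreme, and at a high success rate the effect is a few percentage points. It is an ambiguity to tidy.

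**This could be left to an analysis plan.** The protocol itself fixes the criterion, the exclusion rule, the repeat rule and the end of testing. The difficulty is how these stated rules fit together.

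**Conclusion.** The concern holds in this form: as worded, 6.2.1, 6.2.2 and 6.2.5 allow the failures that 4.0 should count to be excluded and replaced. If a missing control line is an invalid result, the retained rate is 100% at any true first-use rate, whereas on first attempts the chance of passing would be about 0.06 at 90% and 0.18 at 92%. The conclusion rests on the inference from 1.4 and on reading the criterion as 95 of 100; the true rates are assumptions.

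The change of unit within 4.4 is a minor point. Its effect is likely small and depends on an unknown practice effect. The wording should be corrected because the change is cheap and the criterion decides acceptance.

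**What to change.** In 4.0, and consistently in 6.2.1, 6.2.2 and 6.2.5, state that for the 95% control-line rate:

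- each tester's first attempt is scored;
- a first attempt without a control line stays in the denominator as a failure;
- repeats by the same tester are reported separately and do not replace it.

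Define an invalid result in the protocol, so that the exclusion rule and the criterion cannot be applied to the same event in different ways.

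Reword the last sentence of 4.4 so that testing continues until the age range is covered and each section has at least 50 distinct testers, each counted once. The tester forms in 7.2 allow this count.

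Cost: wording only. Each test is already observed and each tester already completes a form, so no new data are needed. The price is a possibly less favourable reported rate and slightly slower recruitment, because one parent could no longer supply several counted units.
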